5.6.3 Compensation Plan for Subjects

Compensation, if any, will be determined locally and in accordance with local IRB requirements and approval.

5.6.4 Costs

There is no cost to subjects for the research tests, procedures/evaluations and study product while taking part in this trial. Procedures and treatment for clinical care including costs associated with hospital stay may be billed to the subject, subject's insurance or third party.

6. STUDY PRODUCT

6.1 Study Product(s) and Administration

Subjects will be randomized into one of two arms (1:1).

Arm 1	Arm 2
Interferon beta-1a SQ injection + remdesivir IV	Placebo SQ injection + remdesivir IV

6.1.1 Study Product Description

Remdesivir component:

Remdesivir is a single diastereomer monophosphoramidate prodrug designed for the intracellular delivery of a modified adenine nucleoside analog GS-441524. In addition to the active ingredient, the lyophilized and solution formulations of remdesivir contain the following inactive ingredients: water for injection, SBECD, and hydrochloric acid and/or sodium hydroxide.

Interferon beta-1a /Subcutaneous Placebo component:

Rebif®, an interferon beta-1a, is a purified 166 amino acid glycoprotein produced by recombinant DNA technology using genetically engineered Chinese Hamster Ovary cells into which the human interferon beta gene has been introduced. The amino acid sequence of Rebif® is identical to natural fibroblast derived human interferon beta.

Rebif® (interferon beta-1a) is formulated as a sterile solution in a prefilled syringe intended for subcutaneous injection. Each prefilled syringe contains 0.5 mL of Rebif®. Each 0.5 mL of Rebif® will contain 44 mcg of interferon beta-1a, 4 mg human albumin, USP; 27.3 mg mannitol, USP; 0.4 mg sodium acetate; and water for injection, USP.

Placebo subcutaneous injection will be either:

- Matching empty syringes that will be filled with 0.5 mL 0.9% normal saline at each site pharmacy; OR

- Matching syringes prefilled with 0.5 mL 0.9% normal saline or 0.5 mL sterile water for injection.

6.1.2 Dosing and Administration

All subjects will receive remdesivir as a 200 mg intravenous (IV) loading dose on Day 1, followed by a 100 mg once-daily IV maintenance dose up to a 10-day total course while hospitalized. Enrollment may proceed for subjects who received one or two doses of remdesivir under EUA or similar mechanism prior to randomization. If subjects already received the loading dose, then start at 100 mg/day on Day 1. Any doses of remdesivir under an EUA (or similar mechanism) within 1 week of enrollment will be counted, so the maximum number of remdesivir doses given to a subject is 10 (i.e. EUA doses + doses on this trial). If one or two doses of remdesivir were administered (under EUA or similar mechanism) prior to study enrollment, this should be documented in eClinical as a concomitant medication given prior to Day 1.

For the subcutaneous interferon beta-1a / placebo component, subjects will receive either active product or placebo as follows:

- Interferon beta-1a will be administered every other day as a 44-microgram subcutaneous dose for a total of 4 doses while hospitalized
- A saline placebo will be administered every other day as a subcutaneous injection for a total of 4 doses while hospitalized

Study teams will instruct the administering nurse to use a different site for each subcutaneous injection. If there is an injection site reaction including skin that is irritated, edematous, reddened, bruised, or necrotic, the study product should not be administered into the affected area. If possible, select a unique site for each subsequent injection.

Dosing of the two medications does not need to occur at the same time.

Duration of therapy:

- IV remdesivir – up to 10 consecutive days while hospitalized (i.e., maximum of 10 total infusions pre-enrollment and during study).
- Subcutaneous (Interferon beta-1a or placebo) component – Days 1, 3, 5, and 7, while hospitalized.
- Both stop on discharge from hospital. If readmitted after discharge, see [Section 7.4](#).

6.1.3 Dose Escalation

Not Applicable

6.1.4 Dose Modifications

The protocol-required safety laboratories (per the SOA) are anticipated to be sufficient for evaluating for dose modifications, but if other laboratory data obtained as part of standard care are available, these should also be used in the evaluation.

Remdesivir component:

Appendix C - ACTT-3: Remdesivir + Interferon Beta-1a

The infusion should be held and not given if the subject is found to have any of the following laboratory values:

- eGFR decreases to < 20 mL/min
 - Remdesivir infusion will be held until the eGFR increases to a point that the potential benefit of giving remdesivir outweighs the potential risk. Note: this is consistent with the FDA Fact Sheet instructions for Health Care Providers, US EUA of Veklury® (remdesivir): "*Veklury is not recommended in adult patients with eGFR less than 30 mL/min...unless the potential benefit outweighs the potential risk*".
- ALT and/or AST increases to > 5 times upper limits of normal (ULN)
 - Remdesivir infusion will be held and not be restarted until the ALT and AST \leq 5 times ULN.

Interferon beta-1a /Subcutaneous Placebo component:

The subcutaneous injection should be held and not given if the subject is found to have any of the following laboratory values:

- ALT and/or AST increases to > 5 times ULN
 - Subcutaneous injection will be held and resume when ALT and AST \leq 5 times ULN.
- Total white cell blood cell count (WBC) <1000 cells/ μ L
 - Subcutaneous injection will be held and resume when WBC \geq 1000 cells/ μ L
- Platelet count <25,000/ μ L
 - Subcutaneous injection will be held and resume when platelet count \geq 25,000/ μ L.

Any dose that is held as described above, may be given later that day if the laboratory parameters improve. Any dose that is missed during the study due to any reason is not made up. The treatment course continues as described above even if the subject becomes PCR negative while hospitalized.

For laboratory values that meet permanent discontinuation thresholds (see [Section 7.1](#)), study product should be discontinued. However, if in the opinion of the investigator, the laboratory abnormality is due to intercurrent illness or another identified factor, laboratory tests may be repeated.

6.1.5 Overdosage

Overdose is not anticipated in the context of a clinical trial. Subjects will be given the subcutaneous injection every other day and daily infusions of remdesivir. No study product will be given after hospital discharge.

6.2 Preparation/Handling/Storage/Accountability

6.2.1 Acquisition and Accountability

Appendix C - ACTT-3: Remdesivir + Interferon Beta-1a

Investigational products (IP) will be shipped to the site either directly from participating companies, from the Sponsor, or from other regional or local drug repositories. All other supplies should be provided by the site. Multiple lots of each IP may be supplied.

Study products received at the sites will be open label and not kit specific, unless specified in the protocol-specific Manual of Procedures (MOP) or pharmacy manual. See the MOP Appendices for detailed information on the preparation, labeling, storage, and administration of investigational products.

Accountability:

The site PI is responsible for study product distribution and disposition and has ultimate responsibility for study product accountability. The site PI may delegate to the participating site's research pharmacist responsibility for study product accountability. The participating site's research pharmacist will be responsible for maintaining complete records and documentation of study product receipt, accountability, dispensation, storage conditions, and final disposition of the study product(s). Time of study drug administration to the subject will be recorded on the appropriate data collection form (CRF). All study product(s), whether administered or not, must be documented on the appropriate study product accountability record or dispensing log. The Sponsor's monitoring staff will verify the participating site's study product accountability records and dispensing logs per the site monitoring plan. Refer to the protocol-specific MOP for details on storing study medications.

Destruction:

After the study treatment period has ended or as appropriate over the course of the study after study product accountability has been performed, used active and placebo product can be destroyed on-site following applicable site procedures with a second staff member observing and verifying the destruction.

Unused product at the end of the study should be saved until instructed by the Sponsor.

6.2.2 Formulation, Appearance, Packaging, and Labeling

Remdesivir component

Remdesivir may be supplied in two formulations:

- The lyophilized formulation of remdesivir is a preservative-free, white to off-white or yellow, lyophilized solid containing 150 mg or 100 mg of remdesivir to be reconstituted with 29 mL or 19 mL (respectively) of sterile water for injection respectively and diluted into IV infusion fluids prior to IV infusion. Following reconstitution, each vial contains a 5 mg/mL remdesivir concentrated solution with sufficient volume to allow withdrawal of 30 mL (150 mg of remdesivir) or 20 mL (100 mg of remdesivir). It is supplied as a sterile product in a single-use, Type 1 clear glass vial. In addition to the active ingredient, the lyophilized formulation of remdesivir contains the following inactive ingredients: water for injection, SBECD, hydrochloric acid, and/or sodium hydroxide. For more information, refer to the MOP.
- The concentrated solution is supplied as a single dose vial containing 100 mg/20 mL (5 mg/mL) of remdesivir per vial for dilution into 0.9% sodium chloride infusion bag. It is a sterile, preservative-free, clear, colorless to yellow, aqueous-based concentrated solution

that is to be diluted into 0.9% sodium chloride infusion bag prior to administration by intravenous infusion. Remdesivir injection, 100 mg/20 mL (5 mg/mL), is supplied in a single-dose clear glass vial. For more information, refer to the MOP and EUA Fact Sheet.

Remdesivir will be labeled according to manufacturer specifications.

Subcutaneous Interferon beta-1a component

Rebif® (interferon beta-1a) is formulated as a sterile solution. It is supplied as a prefilled syringe intended for subcutaneous injection. Each prefilled syringe contains 0.5 mL of Rebif®. Each 0.5 mL of Rebif® will contain 44 mcg of interferon beta-1a, 4 mg human albumin, USP; 27.3 mg mannitol, USP; 0.4 mg sodium acetate; and water for injection, USP.

Subcutaneous placebo component

Placebo will match the active product in appearance. Placebo subcutaneous injection is 0.9% normal saline. The placebo will be supplied as either:

- Matching empty syringes that will be filled with approximately 0.5 mL 0.9% normal saline at each site pharmacy; OR
- Matching syringes prefilled with 0.5 mL 0.9% normal saline or 0.5 mL sterile water for injection.

Study products will be supplied by the sponsor or its designee in accordance with current Good Manufacturing Practice (cGMP).

6.2.3 Product Storage and Stability

The MOP provides instructions for the preparation, handling, and storage of remdesivir. The MOP describes site responsibility and accountability for the administered products. Interferon beta-1a drug product will be described in the package insert. See most recent version of package insert posted on the Emmes website.

6.2.4 Preparation

Refer to the protocol-specific MOP for details about preparation.

Remdesivir is not considered a hazardous drug as defined by NIOSH and ASHP hazard classification systems. The study products may be prepared in a clean room but do not need to be prepared or handled in a fume hood. Measures that minimize drug contact with the body should always be considered during handling, preparation, and disposal procedures as indicated in the IB.

For Rebif® (interferon beta-1a) it is supplied as a close system and therefore no specific handling is required. See MOP for preparing Placebo for Rebif.

6.3 Measures to Minimize Bias: Randomization and Blinding

6.3.1 Randomization

Randomization will be stratified by:

- Site
- Severity of illness at enrollment (by ordinal scale)
 - Hospitalized, requiring supplemental oxygen, or
 - Hospitalized, not requiring supplemental oxygen.

Note: Category 7 (hospitalized, on invasive mechanical ventilation/ECMO) and Category 6 (hospitalized, on non-invasive ventilation or high flow oxygen devices) are not eligible for enrollment. See description of recommendations made by the DSMB on September 4, 2020 below.

The randomization procedure will be described in the MOP.

There was the hypothetical concern that interferon may worsen the pro-inflammatory state seen in COVID-19 late in the clinical course of the disease. For this reason, enrollment was staged based on severity of disease.

- For the first 2 weeks of the study, enrollment was limited to non-intubated, hospitalized COVID-19 patients who meet all eligibility criteria (i.e., patients with baseline ordinal scale score of 4, 5 or 6).
- On September 4, 2020, the DSMB met for an interim safety review of the ACTT-3 data. After their review, they notified NIAID that their recommendation was to close further enrollment to patients with a baseline ordinal score of 6. The DSMB noted there was no increase in mortality in this group, but that the risk/benefit in this group did not warrant further enrollment. Specifically, it was recommended by the DSMB:
 - No further enrollment of subjects with ordinal score of 6 at time of randomization.
 - Do not enroll subjects with ordinal score of 7 at time of randomization
 - Continue to enroll patients with a baseline ordinal score of 4 and 5.
- Furthermore, the DSMB recommended:
 - Subjects currently enrolled who have an ordinal score of 6, should not be given any more study injections (interferon/placebo) for the remainder of the study.
 - Subjects enrolled as a baseline ordinal 4 or 5 and remain as ordinal 4 or 5, should continue to receive study injections (interferon/placebo) and remdesivir per protocol.
 - If a subject is enrolled as a baseline ordinal 4 or 5 and progresses to ordinal 6 or 7, the study injections (interferon/placebo) should be discontinued for the remainder of the study. In this case, the remdesivir infusions would continue per protocol. Importantly, all subjects should remain in the study and followed through day 29 in accordance with the protocol.

6.3.2 Blinding and Masking Procedures

The subcutaneous interferon beta-1a/matching placebo component is blinded. Interferon beta-1a and placebo will be identical in appearance.

Unblinding of the study will occur after all subjects enrolled have reached the end of study, and these visits are monitored and data is cleaned, or if the DSMB recommends unblinding.

Treatment group-level unblinded analyses of subjects randomized in ordinal score category 6 may be conducted and published prior to the end of the trial to communicate the safety signal observed in this group by the DSMB during a safety review. If this analysis is conducted, only members of the unblinded analysis team will have access to subject-level treatment data while the study is ongoing; all other members of the study group will remain blinded to individual subject treatments as originally planned.

If AEs occur and investigators are concerned about the treatment allocation, the treatment can be discontinued. If a Serious Adverse Event occurs, that is thought to be related to the study drug, and the treating clinician believes that knowledge of the treatment arm may change the therapy provided to the patient, the individual subject can be unblinded. The procedure for unblinding will be further detailed in the Manual of Operations.

6.4 Study Intervention Compliance

Each dose of study product will be administered by a member of the clinical research team who is qualified and licensed to administer the study product. Administration and date, and time, will be entered into the case report form (CRF).

6.5 Concomitant Therapy

6.5.1 Permitted Concomitant Therapy and Procedures

Receipt of any exclusionary treatments or medications prior to screening will be assessed at screening to determine eligibility as described in the exclusion criteria. Exclusionary medications include the receipt of convalescent plasma or intravenous immunoglobulin [IVIg]) for the treatment of COVID-19. It also includes small molecule tyrosine kinase inhibitors (e.g., baricitinib, imatinib, gefitinib, acalabrutinib) or monoclonal antibodies targeting cytokines (e.g., TNF inhibitors, anti-interleukin-1 [IL-1], anti-IL-6 [tocilizumab or sarilumab]), or T-cells or B-cells, taken in the two weeks prior to screening for the treatment of COVID-19. Lastly, those who received interferon within 2 weeks of screening either for the treatment of COVID-19 or for a chronic medical condition (e.g., multiple sclerosis, HCV infection) will not be eligible for the study.

For patients that are eligible for the study, other therapy received prior to enrollment with any other experimental treatment or off-label use of marketed medications that are intended as specific treatment for COVID-19 or the SARS-CoV-2 infection (i.e., post-exposure prophylaxis [PEP]) are permitted but must be discontinued on enrollment. There is no waiting period between

Appendix C - ACTT-3: Remdesivir + Interferon Beta-1a

discontinuation of these treatments and administration of study products. However, these prior treatments and their end date should be documented on the Concomitant Medication (CCM) form in the Advantage eClinical system.

Medications used for other non-COVID-19 diseases that also are claimed to be treatments for COVID-19, do not need to be discontinued at the time of enrollment. Examples would include lopinavir/ritonavir for HIV, hydroxychloroquine for lupus, etc. The disease being treated is important: if used as an off-label medication for COVID-19 treatment, they are prohibited; if used for non-COVID-19 diseases, they are allowable.

6.5.2 Prohibited Concomitant Therapy

A subject cannot participate in another clinical trial for the treatment of COVID-19 until after Day 29 (see exclusion criteria).

Once enrolled, concomitant medications for the treatment of COVID-19 as described in written policy or guideline (i.e., not just an individual clinician decision) are permitted. In the absence of a local written standard of care, the National Institutes of Health (NIH) COVID-19 Treatment Guidelines may be used (<https://www.covid19treatmentguidelines.nih.gov/>). This includes anti-inflammatory medications such as dexamethasone and convalescent plasma. Concomitant use of any other experimental treatment or off-label use of marketed medications intended as specific treatment for COVID-19 or SARS-CoV-2 infection, and not specified in the local or NIH COVID-19 Treatment Guidelines are prohibited. Specifically, use of any biologic therapy not specified on the written policy or guideline are prohibited including: monoclonal antibodies targeting cytokines (e.g., TNF inhibitors; interleukin-1[IL-1], IL-6 [tocilizumab or sarilumab]), or T-cells (e.g., abatacept); monoclonal antibodies targeting B-cells (e.g., rituximab, and including any targeting multiple cell lines including B-cells); JAK inhibitor(s) (e.g., baricitinib, imatinib, gefitinib, acalabrutinib); and any type of interferon, convalescent plasma, or immunoglobulin (IgG) therapies for COVID-19. Similarly, the concomitant use of hydroxychloroquine to treat COVID-19 is prohibited unless it is included in the local institutional treatment guidelines.

On August 23, 2020, the FDA issued an EUA for COVID-19 convalescent plasma for the treatment of hospitalized patients with COVID-19. The NIH COVID-19 Treatment Guidelines were updated on September 1, 2020 and concludes that “there are insufficient data to recommend either for or against the use of convalescent plasma for the treatment of COVID-19”. According to the NIH Guidelines and the EUA Fact Sheet for Health Care Providers, convalescent plasma should not be considered the standard of care for the treatment of patients with COVID-19. However, if a site has adopted convalescent plasma as part of their institutional standard of care for the treatment of COVID-19 patients, it is allowed as described above.

Concomitant medications will be assessed from 7 days prior to enrollment to Day 29 or upon discharge, whichever comes first. All prescription medications should be recorded during this time period with the exceptions listed in the bullets below. All medications, except biologics and corticosteroids, can be recorded once regardless of the number of times it was given during the time period. For example, vasopressors should be recorded when first dose given (as the start date) and the last dose given (as the end date) during the period of assessment.

Sites do not need to record any of the following categories of medications in the eClinical system during the period from Day -7 through Day 29:

- All topical medications: ointments, creams, and lotions;
- All intranasal medications: nasal decongestants, nasal allergy medications, nasal steroids, and nasal saline drops/sprays;
- All ophthalmic medications: ophthalmic allergy medication, ophthalmic medications for infection, and ophthalmic medications for eye dryness (e.g., saline eye drops);
- Antiseptic mouth wash, lozenges;
- Cough medication: mucolytics, cough suppressants, and expectorates;
- GI medications: H2 blockers, proton pump inhibitors, GI stimulants, prokinetics, laxatives, stool softeners, antacids, anti-diarrheal and anti-nausea medications;
- Insulin and medications for diabetic control;
- Symptomatic care medications: antipyretics, antihistamines, decongestants, and NSAIDs;
- Vitamins, minerals or herbal supplements, dietary supplements, iron/ferrous sulfate, magnesium, calcium, electrolyte replacement;
- Albumin infusions;
- Melatonin;
- Nicotine patch, lozenge, gum, or nasal spray, or other product to treat tobacco dependence;
- Dyes: iodine – based dye, barium sulfate, and diatrizoate sodium.

See the MOP for more information about recording concomitant medications.

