5.2 Exclusion Criteria

1. Anticipated discharge from the hospital or transfer to another hospital which is not a study site within 72 hours.

2. Subject meets criteria for ordinal scale category 6 or 7 at the time of screening.
3. Subject has a positive test for influenza virus during this current hospital admission.
4. Subjects with an estimated glomerular filtration rate (eGFR) < 30 mL/min are excluded unless in the opinion of the PI, the potential benefit of receiving remdesivir outweighs the potential risk of study participation.
5. ALT or AST > 5 times the upper limits of normal.
6. Total white cell blood cell count (WBC) < 1500 cells/ μ L.
7. Platelet count < 50,000/ μ L.
8. History of chronic liver disease (e.g., jaundice, ascites, hepatic encephalopathy, history of bleeding esophageal or gastric varices). No laboratory testing is needed.
9. Pregnancy or breast feeding (lactating women who agree to discard breast milk from Day 1 until three weeks after the last study product is given are not excluded).
10. Allergy to any study medication including history of hypersensitivity to natural or recombinant interferon beta or human albumin.
11. Patient has a chronic or acute medical condition or is taking a medication that cannot be discontinued at enrollment, that in the judgement of the PI, places them at unacceptable risk for a poor clinical outcome if they were to participate in the study.
12. Received three or more doses of remdesivir, including the loading dose, outside of the study for COVID-19.
13. Received convalescent plasma or intravenous immunoglobulin [IVIg]) for the treatment of COVID-19.
14. Received any interferon product within two weeks of screening, either for the treatment of COVID-19 or for a chronic medical condition (e.g., multiple sclerosis, HCV infection)
15. Received any of the following in the two weeks prior to screening as treatment of COVID-19:
 - small molecule tyrosine kinase inhibitors (e.g. baricitinib, imatinib, gefitinib, acalabrutinib, etc.);
 - monoclonal antibodies targeting cytokines (e.g., TNF inhibitors, anti-interleukin-1 [IL-1], anti-IL-6 [tocilizumab or sarilumab], etc.);
 - monoclonal antibodies targeting T-cells or B-cells as treatment for COVID-19
16. Prior enrollment in ACTT-3

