7.1.1.2 Subcutaneous Interferon beta-1a and Placebo Injections Halting

See [Section 6.1.4.](#) for information about dosing modifications due to laboratory abnormalities.

The subject should not receive any additional subcutaneous injections for the remainder of the study if a subject develops any of the following conditions during the study:

- Disease progresses to the point that the subject requires high-flow oxygen or other non-invasive ventilatory support (i.e., a category 6 on ordinal scale) or mechanical ventilation or ECMO (category 7). Note: even if they improve to a category 4 or 5 before study Day 7, no additional subcutaneous injections will be given.
- Anaphylaxis temporally associated with subcutaneous injection
- Seizures not attributable to COVID-19, a medical complication of COVID-19 or another medical condition
- Thrombotic microangiopathy including thrombotic thrombocytopenic purpura and hemolytic uremic syndrome thought to be due to interferon beta-1a
- ALT or AST >8 times ULN
- Suspected drug-induced liver injury with symptomatic disease (i.e., jaundice, right upper quadrant pain or tenderness, fatigue, nausea, vomiting, etc.)

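### ACTT-3 bans non-study interferon for COVID-19 only where local policy or the NIH guideline does not list it, so open-label use of the randomized drug can be within protocol

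*Protocol*

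**What the plan says.** Appendix C 6.5.2 of the protocol sets the on-study rule for COVID-19 treatments. It starts from a permission: "Once enrolled, concomitant medications for the treatment of COVID-19 as described in written policy or guideline" are allowed, with the NIH guideline as fallback where no local written standard exists. Experimental or off-label treatments outside those sources are banned. The sentence on biologics carries the same condition: "use of any biologic therapy not specified on the written policy or guideline are prohibited including" a list whose last item is "any type of interferon, convalescent plasma, or immunoglobulin (IgG) therapies for COVID-19". The following paragraph then allows plasma "if a site has adopted convalescent plasma as part of their institutional standard of care".

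Four other places bear on non-study interferon:

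- Exclusion criterion 14 (Appendix C 5.2) removes patients who "Received any interferon product within two weeks of screening, either for the treatment of COVID-19" or for a chronic condition.
- Appendix C 6.5.1 says of drugs that also have a non-COVID-19 use: "if used as an off-label medication for COVID-19 treatment, they are prohibited".
- Appendix C 6.3.1 reports the DSMB's advice that on progression to category 6 or 7 "the study injections (interferon/placebo) should be discontinued for the remainder of the study". Section 7.1.1.2 adopts this: even if the patient improves again, "no additional subcutaneous injections will be given".
- SAP 4.2.7 refers back to protocol 6.5.1 and 6.5.2 and adds no rule of its own.

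**The concern.** Interferon beta-1a plus remdesivir against placebo plus remdesivir is the only randomized contrast in ACTT-3. A drug that defines the contrast would normally be barred outright from non-study use in both arms. Here it sits in a general list of biologics whose ban lifts wherever a policy or guideline names the drug. Exclusion 14 goes to some trouble to keep out patients with recent interferon, yet from randomization onward the same drug may be given under local policy.

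Two things would be at stake. The first is the estimate, because controls who receive interferon no longer represent its absence. The second is the DSMB's advice. A patient whose study injections were stopped at category 6 or 7 could be given the same drug open-label, and nothing in the protocol would count that as a deviation.

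**Working it through.** **Step 1: is the ban conditional?** Three features of 6.5.2 agree. The opening permits what a policy or guideline describes. The lead-in to the biologics list bans only what the policy or guideline does not specify. Convalescent plasma, in the same list item as interferon, is expressly allowed where a site has adopted it. Hydroxychloroquine is also conditional on institutional guidelines. Nothing in the section treats interferon differently.

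**Step 2: does any other text close the route?** Exclusion 14 looks back two weeks from screening and says nothing about Day 1 onward. The 6.5.1 sentence concerns which drugs must stop at enrollment; 6.5.2 governs patients once enrolled and contains the guideline exception. Sections 6.3.1 and 7.1.1.2 stop the study injections only. None is an unconditional on-study ban.

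**Step 3: the plan's own figure.** Appendix C 9.2 uses E = 4(1.96 + z)²/{ln θ}². With θ = 1.25 and 85% power, E = 4(1.96 + 1.036)²/(0.2231)² = 721.3, against 723 stated; this reproduces within rounding. The enrollment figure also checks: 831/0.90 = 923.

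**Step 4: dilution, for illustration.** Inverting the formula, power = Φ(ln(ratio)·√E/2 − 1.96). Let c be the share of controls given interferon and f the fraction of the full effect they obtain, so that ln(ratio) = L(1 − c·f). Added interferon in the active arm is taken to have no effect. The documents give no value for c or f; the values below are assumptions. Two starting points are used, both with E = 831:

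- (a) L = ln 1.25 in every stratum.
- (b) Section 9.2 keeps 831 rather than 723 because category 6 is expected to respond less. If that increase is read as just restoring 85% power (our assumption), then L = ln 1.25 × √(723/831), an overall ratio of 1.231.

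| c | (a) ratio, f = 1 | (a) power, f = 1 | (a) power, f = 0.5 | (b) ratio, f = 1 | (b) power, f = 1 | (b) power, f = 0.5 |
|---|---|---|---|---|---|---|
| 0% | 1.250 | 0.896 | 0.896 | 1.231 | 0.851 | 0.851 |
| 5% | 1.236 | 0.863 | 0.880 | 1.219 | 0.813 | 0.833 |
| 10% | 1.222 | 0.825 | 0.863 | 1.206 | 0.770 | 0.813 |
| 20% | 1.195 | 0.730 | 0.825 | 1.181 | 0.670 | 0.770 |

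**Step 5: the opposite sign.** If late interferon harms patients who have progressed, f is negative, 1 − c·f exceeds 1, and the ratio rises above its true value. The Appendix C synopsis raises this possibility: it suggests interferon may have added to inflammation in category 6. The documents give neither the share of controls who progress nor the size of any harm, so no figure is attached. Because the injections are blinded, policy-based use would tend to occur in both arms, which leaves the net direction open.

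**Step 6: what the SAP would catch.** SAP 6.4 plans medications-of-interest sensitivity analyses. Recovery and mortality are censored when the medication starts, and Day 15 status takes the last score before use. Interferon is not named; it could fall under other biologic therapies or the pooled any-medication category. These analyses exclude baseline category 6. The primary mITT log-rank test has no such handling.

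**The case against.** The strongest reply is that no problem has been shown. Any effect needs a policy or guideline that lists interferon, and neither document shows one. Letting sites follow a written standard of care was deliberate. Sites that start interferon early would have made their patients ineligible through exclusion 14, and other prior COVID-19 therapy must stop at enrollment. The closure of category 6 was publicly announced (Appendix C 9.4.7), which makes late open-label use less likely. All of this stands as an argument about extent. It does not change what the text permits.

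A second reply is that safeguards exist. SAP 6.4 allows medication categories to be added after blinded review, biologics are exempt from the record-once rule in 6.5.2, and Appendix C 9.3 lets a committee with the blinded statistical team review medications and deviations. A reader who inferred that the plan ignores such use would therefore be wrong. But these safeguards work after the drug has been given; they neither prevent the use nor protect the primary comparison.

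A third reply is that the power figures are hypothetical. That is so. Shares of 5% to 20% are invented, post-randomization use would probably be later and weaker than a full course, and starting point (b) adds an assumption that section 9.2 does not state.

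**Conclusion.** On the wording the point holds: Appendix C 6.5.2 leaves non-study interferon for COVID-19 within protocol wherever a written policy or the NIH guideline lists it, in either arm and also after injections are stopped. This rests on the text alone.

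The size is unknown and may be nil. Three stronger readings are not supported:

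- That ACTT-3 was contaminated. The documents contain no policy that lists interferon and no record of such use.
- That contamination could only cost power. That follows if the drug helps controls; if it harms those who have progressed, the ratio could move away from 1.
- That the increase from 723 to 831 recoveries is spare margin to absorb dilution. Section 9.2 already commits it to lower efficacy in category 6.

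This is a cheap improvement that protects the trial's one contrast and its DSMB safety measure, not evidence that the result is unsound.

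**What to change.** Remove interferon from the conditional list in Appendix C 6.5.2 and add:

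> Non-study interferon given for COVID-19 is prohibited in both arms from randomization through Day 29, including during any readmission, regardless of local policy or guideline; any known use is recorded as a protocol deviation, and the subject remains in follow-up and in the mITT analysis.

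The ban should not end at discharge, because section 7.4 allows study injections to resume on readmission before Day 8. Optionally, name non-study interferon as a subcategory in SAP 6.4 and in Tables 51 and 52.

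The cost is one protocol sentence and, if wanted, one SAP subcategory. A site whose policy lists interferon could not give it to enrolled patients for COVID-19. Outpatient use after discharge would stay largely unverified, since 6.5.2 ends medication recording at Day 29 or discharge, whichever is first; hence the word known. SAP 9.1.2, which ends the medication history at about Day 15, should be aligned with the protocol. Interferon for other diseases is untouched.
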